#### 9.8.3. Nodule Characteristics

Nodule characteristics (e.g., size, location, morphology) will be captured at procedure.

#### 9.8.4. Index Procedure

The index procedure workflow is shown in Figure 2. The EWC will be inserted and navigation to the target will be conducted according to the manufacturer's Instructions for Use.

CBCT will be used to confirm target nodule localization using fluoroscopy overlay. If CT indicates the absence of a bronchus sign leading to the center of the target nodule, access to the nodule may be obtained using the CrossCountry™ Transbronchial Access Tool under CBCT guidance.

During the index procedure imaging, nodule eligibility criteria will be re-confirmed. Any patients with nodules no longer meeting eligibility criteria will not be enrolled. For the purpose of this clinical study investigational plan, the point of enrollment is defined as the insertion of the Emprint™ Ablation Catheter Kit with Thermosphere™ Technology into the EWC.

A high-level procedure workflow is shown below. Investigators will refer to the manufacturer's instructional documents for additional detail.

MDT18010ILSBA

Version 4.0 2

26-SEP-2019

Page 27 of 50

Medtronic

[figure not shown]

Figure 2. Index procedure workflow

#### 9.8.5. Safety Endpoints

The primary objective of this prospective, single-arm, multicenter, non-randomized study is to characterize the safety of the Emprint™ Ablation Catheter Kit with Thermosphere™ Technology device in subjects undergoing lung ablation procedures.

The primary endpoint is the composite rate of AEs related to the Emprint™ Ablation Catheter Kit with Thermosphere™ Technology through 1-month follow-up.

In addition, the following secondary safety endpoints will be evaluated:

- Composite rate of SAEs related to the Emprint™ Ablation Catheter Kit with Thermosphere™ Technology through 1-month follow-up.
- Composite rate of all AEs related to the procedure or study devices through 1-month follow-up.
- Composite rate of all SAEs related to the procedure or study devices through 1-month follow-up.

All AEs related to the Emprint™ Ablation Catheter with Thermosphere™ Technology will be graded for severity based on the Common Terminology Criteria for Adverse Events.

MDT18010ILSBA

Version 4.0

26-SEP-2019

Page 28 of 50

For safety reporting, only AEs related to the Emprint™ Ablation Catheter Kit with Thermosphere™ Technology, accessory devices, or study procedures will be captured and reported until the subject exits the study (refer to Section 11.1 for additional details). Related AEs will be summarized as the event counts and percentage which occurred during the ablation procedure or detected after the procedure within the 1-month reporting timeframe. For the primary endpoint, relationship specifically to the Emprint™ Ablation Catheter with Thermosphere™ Technology device will be assessed.

#### 9.8.6. 1-Month Follow-Up

The study subject will complete the study at the conclusion of the 1-month follow-up visit, conducted per standard local practice, but within the window of 20-40 days after the study index procedure.

The following assessments will be performed and the results recorded on the appropriate subject eCRFs:

- Medication use (e.g., immunotherapy, chemotherapy, targeted antineoplastic therapy, prescription antithrombotics)
- A follow-up CT scan at this timepoint will be used for the evaluation of Technique Efficacy
- AE assessment (AEs related to the Emprint™ Ablation Catheter Kit with Thermosphere™ Technology, accessory devices, or study procedures)
- Quality of life survey (EQ-5D)
- Bronchoscopic Ablation Patient Pain and Satisfaction Survey

#### 9.8.7. Study Completion

Subjects will complete the study at the completion of the 1-month post-procedure visit. No additional study-specific care will be provided to study subjects after completion of the study. Standard of care should continue. The reporting window for the 1-month follow-up is 20-40 days.

# 9.9. Recording Data

This study will utilize an eCRF. The eCRF will be used to capture the required data elements. Medical and study records, rather than eCRFs, will serve as the source documentation.

# 9.10. Deviation Handling

No written waivers from the CIP will be granted. The Principal Investigator must make every effort to follow the CIP, unless the deviation is necessary in an emergent situation to protect the rights, safety and/or well-being of the subject. Deviations from the CIP will be collected on a Protocol Deviation CRF and reviewed with the Principal Investigator to ensure compliance.

The investigator must notify Medtronic and the reviewing ethics committee (EC) / institutional review board (IRB) of any deviation from the Investigational Plan when specific to the protection of the life or

MDT18010ILSBA

Version 4.0

26-SEP-2019

Page 29 of 50

physical well-being of a subject in an emergency. Such notice must be given as soon as possible, but in no event later than five (5) working days after the emergency has occurred. All study deviations will be reported by Medtronic to the Regulatory Authority (if applicable) via either Final Clinical Study Report or separate notification in case of substantial CIP deviation, for which the Regulatory Authority approval is required before its implementation.

If a pattern of non-compliance is noted, the study manager will determine the course of action to take, such as root cause, review relevant CIP procedures and as applicable retrain and verify understanding of the issue in question. This will be documented in the Study Master Files. In the case of repeated or serious non-compliance, the Sponsor reserves the right to disqualify the offending site.

#### 9.11. Subject Withdrawal or Discontinuation

Subjects may voluntarily withdraw from the study if they no longer wish to have their study-related information used. Additionally, the Principal Investigators may withdraw or choose not to enroll subjects if they feel they do not meet the CIP defined inclusion and exclusion criteria or if it is in the best medical interest of the subjects in question.

In cases of voluntary subject withdrawal, all data collected from the time of informed consent to the time of voluntary withdrawal may be used. The General Data Protection Regulation (GDPR) process will be followed as applicable per country regulations. Withdrawn subjects will not be replaced. Enrollment will continue as per CIP definitions up to the predefined maximum number of subjects.

All subjects will be followed per institutional standard of care after any withdrawal, discontinuation, or completion of the study follow-ups.

The reason for study exit of all enrolled subjects will be documented on the applicable electronic case report form (eCRF). In the event the subject withdraws consent during the study, the date of withdrawal will be documented. If the study investigator voluntarily removes a subject from further study participation, supporting documentation must be in place for the rationale and date of removal. Every attempt will be made to contact subjects who are noncompliant. Subjects will be considered lost to follow-up once the following steps have been taken:

- Three phone calls should be made to the subject. Each attempt should be clearly documented in the source documents and the response or lack thereof should be captured.
- If there is no response to the phone calls, then a certified/registered letter should be written to the subject. A copy of the letter should be retained in the subject's source document.
- After a period of one week following completion of the above actions, the subject will be considered lost to follow-up. The sponsor should be notified and the Study Exit form should be completed.

MDT18010ILSBA

Version 4.0 26-SEP-2019

Page 30 of 50

#### 10. Risks and Benefits

#### 10.1. Potential Risks

The potential risks of the Emprint™ Ablation System have been described in the Risk Management Report for the Emprint Ablation System with Ablation Catheter and the Clinical Evaluation Report for the Covidien Emprint™ Ablation System and Accessories and are summarized briefly below. The clinical investigation has been designed to involve as little pain, discomfort, fear, and any other foreseeable risk as possible for the subjects, and both the risk threshold. The degree of distress are specifically defined in the clinical investigation plan and constantly monitored.

#### 10.1.1. Summary of Risk Management Report

A clinical risk/benefit analysis evaluated whether the Emprint™ Ablation System with Ablation Catheter is likely to provide more benefit than harm. Listed below are the high-risk residual risks from the risk analysis. All of the residual risks listed below have been described in the literature as known and/or experienced complications of ablation procedures. All patients who undergo an ablation procedure are consented for such risks. Benefit estimation describes the expected performance of the device, expected clinical outcome, and risks and benefits related to other procedural options. The risk/benefit comparison documents the judgments of whether the benefits exceed the residual risks.

- Pleural effusion
- Intraparenchymal pulmonary hemorrhage / bronchopulmonary hemorrhage
- Pain/shoulder pain
- Mortality
- Pyothorax
- Atrial fibrillation
- Hemolysis
- Pulmonary/upper respiratory fistula
- Hemothorax
- Abscess
- Hematoma
- Hemoptysis
- Pneumonia
- Pulmonary edema
- Ventricular arrhythmia
- Unintended microwave burn unintended tissue ablation
- Unintended microwave burn vessel thrombosis /thrombus /embolism

MDT18010ILSBA

Version 4.0

26-SEP-2019

Page 31 of 50

Unintended microwave burn – diaphragmatic paresis

Expected AE rates are described in Section 10.1.2 below.

In accordance with the safety assessments described in Section 9.8.5, risks will be continuously monitored, assessed and documented by the investigator.

#### 10.1.2. Summary of Clinical Evaluation Report

A Clinical Evaluation Report (CER) for the Covidien Emprint™ Ablation System and Accessories was performed according to the provisions of the Medical Devices Directive 93/42/EEC (MDD), as amended by Directive 2007/47/EC. This report was prepared in accordance with the following Guidelines and Standard Operating Procedures (SOPs) to provide evidence of the medical safety and performance of the Emprint™ Ablation System and Accessories for its intended use: MEDDEV 2.7/1 rev. 4 (June 2016), MEDDEV 2.12/2 rev. 2 (January 2012). The intent of this CER was to provide evidence that the Emprint™ Ablation System and Accessories are safe, effective, and state-of-the-art for the indications and intended use, through a critical review of product-related documents, testing, published clinical literature and post-market data. A brief summary of that report is included below.

The safety of the Emprint™ Ablation System has been assessed in 8 clinical studies evaluating its use in the liver,  pancreas,  and lung,  as well as complaints and vigilance reports of 27,150 devices sold. All complications occurred in < 1% of patients each (total complication rate 4.7%). This is comparable to or better than the 10.3% complication rate in the liver for minor and major complications reported in the literature. The majority of complications reported with use of microwave ablation in the lung (such as pneumothorax and hemorrhagic effusion) were from one clinical publication and one clinical investigation and are either known complications of microwave ablation or were deemed to not be related to the device or the procedure. In one clinical publication of microwave ablation in the pancreas, pain was the only complication reported. Pain is a common complication, and often resolves spontaneously or with treatment.

In the post-market complaints and vigilances report spanning a 5-year period, all confirmed injuries are known to occur with microwave ablation. In addition, 5 of 7 deaths reported occurred in patients with major comorbidities.

All complications that occurred with use of the Emprint™ MWA ablation system in the liver, lung, and pancreas are either known to occur with microwave ablation or were deemed to be unrelated. In addition, complications in the liver and lung occurred at similar rates to other microwave ablation devices reported in the literature.

#### 10.1.3. Radiation Exposure

There are risks associated with the use of x-ray fluoroscopy, CBCT, and CT imaging for this study.

MDT18010ILSBA

Version 4.0

26-SEP-2019

Page 32 of 50

The CT scan and the imaging that will be carried out as part of the ablation procedure are part of the patient's routine care. These procedures use ionizing radiation to form images of the body and provide the doctor with other clinical information. Ionizing radiation can cause cell damage that may, after many years or decades, turn cancerous. The chances of this happening are the same whether patients take part in this study or not. It should be noted that radiation dose will vary based on the type of imaging system used and the size of the patient.

#### 10.2. Potential Benefits

Benefit estimations of the general use of the Emprint™ Ablation Catheter with Thermosphere™ Technology are described in the Risk Management Report for the Emprint™ Ablation System with the Ablation Catheter.

Microwave ablation is an alternative for patients with lung cancer who are either ineligible for or refuse other treatments such as surgical resection. Furthermore, bronchoscopic ablation may result in fewer complications than percutaneous ablation (see Section 4.1). For patients who are not candidates for alternative therapies, the benefits of microwave ablation outweigh the risks described above.

The bronchoscopic ablation procedure described in this study is commercially available. Patients could receive these potential benefits without taking part in the study and may not gain any direct medical benefits compared to routine care. However, the data collected from this study will help characterize the safety and performance of the Emprint™ Ablation Catheter with Thermosphere™ Technology. If the results of this study support additional clinical research, further studies may be justified to evaluate the potential for improved standard-of-care using microwave ablation technology in lung nodules.

#### 10.3. Risk-Benefit Rationale

As described in the Risk Management Report for the Emprint™ Ablation System with the Ablation Catheter, performing image-guided microwave ablation involves risk. Complications have been reported in the literature associated with thermal ablation of the lung. These complications are associated with both the intervention itself and patient comorbidity. For patients who are not candidates for alternative therapies, the benefits of microwave ablation described above outweigh these risks.

#### 11. Adverse Events and Device Deficiencies

# 11.1. Definitions/Classifications

Adverse event (AE) definitions used in this study are based on ISO 14155:2011 (Clinical Investigation of Medical Devices for Human Subjects -- Good Clinical Practice;

https://www.iso.org/obp/ui/#iso:std:iso:14155:ed-2:v1:en), which is aligned with MEDDEV 2.7/3

MDT18010ILSBA

Version 4.0

26-SEP-2019

Page 33 of 50

Revision 3, May 2015 (Guidelines on Medical Devices, Clinical Investigations: Serious Adverse Event Reporting).

For the purpose of this clinical study investigational plan, the point of enrollment is defined as the insertion of the Emprint™ Ablation Catheter Kit with Thermosphere™ Technology into the EWC. AEs will be collected beginning at the point of enrollment. For safety reporting, only AEs related to the procedure or study devices will be captured and reported until the subject exits the study. Any unresolved procedural or device related events that are still ongoing past study exit will be monitored by the physician per their institutional standard-of-care.

Anticipated AEs are listed in Section 10.1.

AEs related to the Emprint™ Ablation Catheter Kit with Thermosphere™ Technology, accessory devices, or study procedures will be adjudicated by an independent medical monitor.

Refer to the NAVABLATE Adverse Event Reference List (Appendix 17.5) for additional definitions.

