### 9. Study Procedures

Following confirmation of eligibility and informed consent, subjects with inoperable lung nodules will undergo an ablation procedure using a bronchoscopic approach. A target nodule will be identified on a pre-procedure CBCT scan. Nodule localization will be aided by ENB using the superDimension™ navigation system. Once localized, if no suitable bronchus sign leads to the proposed area to ablate, access to the region may be obtained using the CrossCountry™ Transbronchial Access Tool. Once ablation region access has been achieved, the ablation catheter will be placed inside the EWC and will be unsheathed inside the target nodule. Correct positioning will be verified using CBCT and the nodule will then be ablated. AEs related to Emprint™ Ablation Catheter Kit with Thermosphere™ Technology, accessory devices, or study procedures will be captured and reported until the 1-month follow-up visit.

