#### 9.1. Schedule of Events

Variables to be collected (following confirmation of eligibility and written informed consent), follow-up visit schedule, and tests to be performed at each visit are described in **Table 1** below.

MDT18010ILSBA Version 4.0 26-SEP-2019

Page 23 of 50

Table 1. Schedule of Events.

	Baseline (Day -30 to Day 0)	During the Procedure and Immediately Post- Procedure	1-Month Follow-up (20 to 40 Days Post- Procedure)
Subject demographics	Х		
Medical history (Lung Diagnoses, Previous Lung procedures, Lung function tests, etc.)	Х		
Eligibility assessment	Х	Х	
Nodule characteristics		Х	
Procedural information		Х	
Adverse event assessment		Х	Х
Imaging	X*	Х	Х
Concomitant medications	Х	Х	Х
Quality of life survey (EQ-5D)	Х		Х
Bronchoscopic Ablation Patient Pain and Satisfaction Survey			Х

\*Standard-of-care CT scan performed prior to consent.

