# 9.2. Subject Screening

A baseline visit will be performed within 30 days prior to the scheduled procedure to assess study eligibility. During the index procedure imaging, nodule eligibility criteria will be re-confirmed. Consented subjects will be considered for the study if they meet specified inclusion criteria and none of the exclusion criteria. The criteria for enrollment must be followed explicitly.

Subjects who provide study consent, but then are determined to be ineligible prior to the start of the ablation portion of the procedure will be considered screen failures and will not require additional study follow-up visits. The reason for the Screen Failure will be clearly documented on the applicable electronic case report forms (eCRFs). Screen failures will not be counted towards the number of study subjects.

MDT18010ILSBA

Version 4.0

26-SEP-2019

Page 24 of 50

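### Adverse event collection opens at ablation catheter insertion, but two secondary safety endpoints count events from navigation bronchoscopy and anaesthesia, which start earlier

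*Protocol*

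**What the plan says.** Protocol 11.1 is the only place that gives an explicit start: "AEs will be collected beginning at the point of enrollment". Enrolment is defined as insertion of the ablation catheter kit into the EWC, both there and in Protocol 8.2, 9.8.4 and 14.1 and SAP 7.1.1 and 7.1.2.

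That moment falls well into the session. Protocol 9.8.4 begins with "The EWC will be inserted and navigation to the target will be conducted", followed by cone-beam CT confirmation and, if needed, transbronchial access. Protocol 9 gives the same order: "Once ablation region access has been achieved, the ablation catheter will be placed inside the EWC".

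SAP 7.7.2.2 counts an AE if any one of six relatedness questions is answered yes: ablation catheter, ENB procedure, ablation procedure, anaesthesia, navigation system or positioning tool. SAP 7.7.2.3 is the same rule restricted to serious events.

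Other text sets no start at insertion:
- Protocol 9 says AEs related to the catheter kit, "accessory devices, or study procedures will be captured and reported until the 1-month follow-up visit".
- The row "Adverse event assessment" in Protocol Table 1 (repeated in SAP Table 1) is ticked for the whole procedural column.
- Protocol 9.8.5 summarises related AEs "which occurred during the ablation procedure or detected after the procedure within the 1-month reporting timeframe".
- Protocol 11.2.1 makes any AE related to the kit, accessory devices or study procedures reportable.
- SAP 7.2 undertakes to collect and report AEs for all enrolled subjects.

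For sessions that end before insertion, Protocol 9.2 says that consented subjects found ineligible "will be considered screen failures and will not require additional study follow-up visits", and that "Screen failures will not be counted towards the number of study subjects". Protocol 9.11 also lets the investigator decline to enrol a subject on medical grounds.

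**The concern.** The study sets out to describe the safety of the bronchoscopic ablation procedure, and these two secondary endpoints are the ones meant to cover the whole session. Their exposures (anaesthesia, navigation, access) begin before the window in 11.1 opens. A site that follows 11.1 to the letter would not record an access or anaesthesia complication noticed before the catheter goes in, even though the SAP has relatedness questions for it. Any such omission works in one direction, towards a more favourable rate. With about 20 to 30 subjects, one case can decide whether a reported rate is zero.

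**Working it through.** The documents give no figure to reproduce; this is mainly a comparison of rules.

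**1. Which relatedness items can arise before insertion.** Anaesthesia, the ENB procedure and the navigation system clearly can. The catheter and the ablation itself essentially cannot. The catheter-related primary endpoint and the catheter-related serious AE endpoint therefore lose little or nothing from their numerators.

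**2. Where a loss would occur.** It would be at collection, not analysis. The SAP counts days to an event from the procedure date, so a same-day event, once recorded, is not removed by date. The rules in SAP 7.7.2.1 to 7.7.2.3 break off after a final conjunction in the text available. Whatever condition follows, it cannot restore an event that was never collected.

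**3. Effect by type of subject, with N = enrolled subjects (SAP 7.1.2).**

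| Subject | In N? | Effect of literal 11.1 |
|---|---|---|
| Related AE recognised before insertion, then enrolled, no other counted AE | Yes | Subject lost from the numerator; rate falls |
| Same, but with another counted AE | Yes | Subject rate unchanged; event count falls |
| AE begins before insertion, detected after it, enrolled | Yes | May still be recorded (Protocol 9.8.5) |
| Session stopped before insertion | No | Rates unchanged; AE not described anywhere |

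Only the first row moves the subject-level rate, which SAP 7.2 makes the primary analysis.

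**4. Size per subject.** Losing m such subjects lowers the rate by m/N. For m = 1:
- N = 30 (planned maximum): 1/30 = 3.3% becomes 0/30.
- N = 20 (approximate minimum): 1/20 = 5.0% becomes 0/20.

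For scale only, since SAP 7.7 plans an exact interval for the primary endpoint alone, the two-sided 95% Clopper-Pearson upper limit would fall from 17.2% to 11.6% at N = 30 and from 24.9% to 16.8% at N = 20.

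**5. How likely a loss is.** The documents do not say what share of related AEs is recognised before insertion. As an illustration, take the 3.1% pneumothorax rate that Protocol 4.1 cites for navigation bronchoscopy. Let f be the assumed share recognised before insertion in subjects who are still enrolled. Then P(at least one lost) = 1 − (1 − 0.031f)^N.

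| f | N = 20 | N = 30 |
|---|---|---|
| 0% | 0% | 0% |
| 25% | 14% | 21% |
| 50% | 27% | 37% |
| 100% | 47% | 61% |

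At N = 30 and f = 100% the expected number lost is 30 × 0.031 = 0.93. The range is wide because f is unknown, so this is not an estimate.

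**6. Wording of N.** SAP 7.7 takes N as subjects with an ENB index procedure; SAP 7.1.2 uses enrolled subjects. These coincide if the index procedure means the ablation, or if stopped sessions are screen failures outside the subject count. If one stopped session were added to 30 enrolled subjects, the primary upper limit with zero events would be 1 − 0.025^(1/31) = 11.2% instead of 1 − 0.025^(1/30) = 11.6%.

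**The case against.** The strongest reply is that sites would collect these events anyway. Protocol 9, both assessment tables, Protocol 11.2.1 and SAP 7.2 set no start at insertion, and the relatedness questions name anaesthesia and the navigation bronchoscopy. The enrolment point is also an openly declared departure from ISO 14155 in Protocol 14.1. The study is descriptive, with no hypothesis or threshold, so no formal decision turns on zero versus one.

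Much of this stands. A reader might infer that the protocol definitely excludes AEs before insertion in enrolled subjects. The documents do not support that: they conflict, and the weight of the other text is towards capture.

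It does not dispose of the point. Protocol 11.1 is the only explicit start rule, and the competing passages are silent on start rather than overriding it. Protocol 9.8.5 does not settle the matter, because it speaks of the ablation procedure while SAP 7.7.2.2 lists the ENB and ablation procedures separately. Protocol 14.1 declares the enrolment point but not its consequence for these endpoints.

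A second reply rests on Protocol 11.1.7, which treats complications of procedures as unrelated if those procedures would have been applied without the device. Read broadly, that could remove navigation complications altogether. But SAP 7.7.2.2 counts them expressly, so this is a further inconsistency to reconcile.

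A reader might also infer that sessions stopped before insertion lower the two rates. They do not: with N = enrolled, those subjects are in neither numerator nor denominator. The reporting route in Protocol 11.2.1 does not expressly cover subjects who were never enrolled, so their AEs remain a gap in the safety description.

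**Conclusion.** Wrong as written, of modest severity: the stated collection rule does not match two stated endpoints. For a subject later enrolled, literal use of Protocol 11.1 omits a related AE recognised before insertion and can only lower the two secondary rates covering the procedure or study devices. The effect is 3.3 points per lost subject at N = 30 and 5.0 points at N = 20, provided the subject has no other counted event. How many would be lost is unknown and may be none, since other sections point towards capture.

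It would go too far to say that the primary endpoint is biased. Its numerator concerns the catheter and is essentially unaffected, and the wording of N in SAP 7.7 is a near-null alignment matter. For stopped sessions the defect is an incomplete safety description, not a change in the rates.

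**What to change.** Keep the enrolment definition and make these changes:
- **Protocol 11.1:** collect related AEs from the start of the index session (anaesthesia or bronchoscopy, whichever comes first) in consented subjects.
- **Alignment:** bring Protocol 9, Table 1 and 9.8.5, and SAP 7.1.1 (Table 1) and 7.2, into line with that start.
- **Relatedness:** reconcile Protocol 11.1.7, on complications of procedures that would have been applied anyway, with the items in SAP 7.7.2.2 and 7.7.2.3.
- **Stopped sessions:** report separately the number of sessions stopped before insertion, whatever the reason, with their related AEs. State the collection window for these subjects, because Protocol 9.2 gives screen failures no follow-up visits.
- **Minor wording:** in SAP 7.7, set N to enrolled subjects for all four safety endpoints, as in SAP 7.1.2.

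The cost is a protocol amendment with the ethics committee and regulatory approvals in Protocol 15.6, matching SAP edits, and AE forms for a few subjects who have already consented. Protocol 8.2 already documents screen failures in the database. Enrolled subjects need no extra visits. The procedure-related rate may come out slightly less favourable.
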